### 3.3. Selection of Clinical Trial Population

North Cliff Consultants will recruit children meeting the inclusion/exclusion criteria from their Cincinnati database.

#### 3.3.1 Inclusion Criteria

Inclusion and Exclusion criteria will be assessed at the Enrollment visit in an individual conversation with parent/legal guardian (with child present).

Subjects are eligible for enrollment if the parent/legal guardian responds positively ("Yes") to the following questions:

- INCL01:** Have you read and understood the Informed Consent document?
- INCL02:** Is your child generally healthy? [excluding acute conditions such as flu/cold symptoms, diarrhea, fever, ear infection, etc.]
- INCL03:** Is your child 4-7 years of age?
- INCL04:** Does your child weigh approximately 37–63 pounds and fit into the test pant [Clinical trial personal to confirm fit]?
- INCL05:** Thinking of the past 3 months, does your child wet the bed at night at least once per week?
- INCL06:** Is your child currently using overnight pants or diapers?
- INCL07:** Is your child willing to use their usual and/or supplied overnight pant products every night for the duration of the study?
- INCL08:** Are you and your child willing to refrain from using wet wipes in the pant area for the duration of the clinical trial?
- INCL09:** Are you willing to refrain from enrolling your child in other clinical or consumer studies for the duration of this clinical trial?
- INCL10:** Are you and your child willing to refrain from using lotions, creams, ointments, oils, moisturizing bubble baths, powders, sunscreen and/or skin preparations in the child's pant area and on thighs for the duration of this clinical trial, unless required for medical reasons?
- INCL11:** Are you and your child willing and able to comply with all study instructions?
- INCL12:** Do you have an iPhone 7 (or higher) with iOS 13.0 operating system (or higher) or do you have an Android smartphone with operating system Android 9 (or higher) installed?
- INCL13:** [REDACTED]
- INCL14:** Are you able to fill in the required questionnaires in English?
- INCL15:** Are you willing to complete the [REDACTED] questionnaires twice daily for 6 weeks, once in the morning when removing the pant and once more in the evening when applying the pant?

### 3.3.2 Exclusion Criteria

Subjects are ineligible for enrollment if the parent/legal guardian responds positively ("Yes") to any of the following questions:

- EXCL01:** Does your child have any acute or chronic skin conditions (excluding skin rash) in or around the pant area?
- EXCL02:** Does your child currently have (or have a history of) any significant illness or chronic medical condition (SITE: that in the opinion of the investigator may negatively impact child's health and/or clinical trial results, for example medications to treat nocturnal enuresis, antibiotics, antihistamines, anti-inflammatory medications, corticosteroids, medications to treat yeast infection or similar)?
- EXCL03:** Is your child currently using any medications? (SITE: that in the opinion of the investigator may negatively impact child's health and/or clinical trial results)?
- EXCL04:** Does your child currently wear absorbent products during the day?

**EXCL05:** Does your child suffer from any other lower urinary tract symptoms (e.g., increased frequency, daytime incontinence, urgency, genital, or lower urinary tract pain) or a history of bladder dysfunction?

### 3.3.3 Compliance and Habits & Practice Questions

The following questions will be asked twice daily (am/pm) [REDACTED]:

1. Did your child experience any of the following health conditions since you last completed the questionnaire: diarrhea, fever, other illness, injury, or none of the above?
2. Has your child taken, or did you apply any of the following since you last completed the questionnaire: vaccination, medication, or none of the above?
3. Did your child bathe since you last completed the questionnaire?
4. Did your child swim since you last completed the questionnaire?
5. Did you or your child use cosmetics in the pant area since you last completed the questionnaire (lotion, oil, cream, powders, sunscreen, moisturizing bath additives, wet wipes, etc.)?
6. Which pants did you use since you last completed the questionnaire?

### 3.3.4 Data Measurement Collection

The following information will be collected twice daily (am/pm) [REDACTED]:

1. Leaks (If yes, parent/legal guardian will be asked to take an image of the wet stain on the pant and send the image to the site) [REDACTED]
2. [REDACTED]
3. [REDACTED]
4. [REDACTED]
5. Photos of pant on child [left hip, right hip, front, back] [REDACTED]
6. Parent/child assessment of rash [hips, genital, buttock, perianal] [REDACTED]
7. [REDACTED]
8. Pant weight (loaded pant mornings / fresh pant evenings)
9. Hours of pant wear
10. Pant contents [urine, both urine & BM, parent removed solid BM, nothing]
11. Number of pants used since last questionnaire
12. Observations during pant removal: [REDACTED]

## 3.4 Subject Identification

The 4-digit unique panelist number in addition to their 3-letter code will identify subjects throughout the clinical trial. Boy subjects start with 1001 and girl subjects start with 2001. Each panelist will also get a 3-letter code to help identify them in case they accidentally enter a wrong subject number.

## 3.5 Subject Accountability

A Subject Accountability form will be completed at visit 3 for all subjects enrolled into the clinical trial.

### **3.5.1 Removal of Subjects from the Clinical Trial**

Participation in this clinical trial is completely voluntary. After admission to the clinical trial, the subject may withdraw at any time for any reason and will be asked to report such reason fairly and accurately. The Principal Investigator or clinical trial representative may elect to discontinue a subject's participation at any time if they deem it necessary or if it is in the subject's best interest. Reasons for subject withdrawal or discontinuation will be documented in Subject Accountability.

### **3.5.2 Replacement of Subjects**

If a subject drops out of the clinical trial, they will not be replaced, due to the short duration of the clinical trial.

## **3.6 Products**

All participants will be asked to use either their current night pant product or the NJ EU pant product during the clinical trial (order based upon randomization).

**Test product:** Ninjama S7 [REDACTED] product produced in Targowek plant in Poland [REDACTED]  
[REDACTED]

**Own product:** Any disposable overnight pant/diaper, disposable training pant/diaper or reusable cotton pant/diaper available on the market for children age 4-7. Parent/legal guardian will purchase and use their own overnight pant as agreed upon in the enrollment visit. They will be asked not to switch brands during the 3 weeks they use their own product. Lot codes of own product will be documented.

## **3.7 Assessment and Collection Details**

### **3.7.1 Skin Rash [REDACTED] Grading [REDACTED]**

The parent/legal guardian will use the following multi-level grading scale to assess rash [REDACTED] in the following regions of the pant area: hips, genital area, buttock area, perianal area (only rash grading):

- None
- Mild
- Moderate
- Severe

### **3.7.2 [REDACTED]**

**3.7.3** [REDACTED]

[REDACTED]

[REDACTED]

[REDACTED]

[REDACTED]

**3.7.4 Pant Weight/Wear Time** [REDACTED]

Pant weight will be measured on a kitchen scale after pant removal. Pant wear time will be recorded in the mornings. Both measurements will be recorded [REDACTED].

**3.7.5** [REDACTED]

[REDACTED]

[REDACTED]

**3.7.6 Photos** [REDACTED]

Photo images will be taken by parent/legal guardian to collect images of the pant fit [REDACTED]

[REDACTED]

Parent/legal guardian will also be asked to take an image of wet stains in the pajama pant, so we can determine where the leak happened and how big the stain was. Images should be taken of the pant on the child in the crotch area, front, back or sides, depending on where the stain is.

Photos will be stored without personally identifiable information and in such a manner as to restrict access through password protection. [REDACTED]

[REDACTED]

Images will be assessed by an expert grader to look for potential incorrect use of the product (e.g., worn the wrong way) [REDACTED].

### **3.7.7 Twice Daily Questionnaire [REDACTED]**

Parent/legal guardian will be asked questions twice daily (once in the morning when removing the night pant and once in the evening when applying the fresh night pant) regarding [REDACTED] [REDACTED] their perception of skin rash [REDACTED]. They will be asked to take photos, [REDACTED] and answer questions about the child's H&P and overall health. [REDACTED]

### **3.7.8 Skin Irritation Perception**

Child will be asked their perception of skin irritation by picking one of the following options. If they pick an option, they will be asked where they feel the irritation.

- Nothing
- Skin is burning/stinging
- Skin is itching/tingling
- Skin is feeling warm/hot

## **4. Statistical Methods**

### **4.1 Statistical Analysis**

All statistical analyses will be the responsibility of the Sponsor. A separate statistical analysis plan is in Attachment B.

### **4.2 Determination of Sample Size**

This data will be used to bridge to a wealth of existing P&G Baby and FemCare AI clinical trial data, therefore sample size was based on practical limitation, not on statistical considerations.

## **5. Risk Assessment- See Attachment A**

## **6. Conduct of the Clinical Trial**

### **6.1 Protocol Amendment(s)**

No amendments to the protocol will be permitted without approval from both the Sponsor and Principal Investigator and where applicable, the Ethics Commission. Such changes and the reasons for those changes will be documented in writing and signed by the Principal Investigator if required. Approval by the Ethics Commission (if applicable) must be obtained prior to initiation of the amendment.

The Principal Investigator, the project manager or their designee will communicate any deviations from the protocol to the Sponsor as soon as possible. The Principal Investigator is responsible for documenting any deviation in the clinical trial file and in the final report.

## 7. Obligation of the Investigator

This clinical trial will be conducted in accordance with the applicable ISO 14155 Clinical Investigation of Medical Devices for Human subjects – Good Clinical Practices (GCPs) and GCPs according to the International Conference on Harmonization (ICH). The Principal Investigator will perform or directly supervise the performance of all the services described herein, or incidental to those described herein, in accordance with the highest standards of medical and clinical research practice. Delegation of any clinical trial responsibility will be documented in writing. The Investigator will also be required to submit a report documenting clinical trial execution.

### 7.1 Adherence to Protocol

The Investigator will have responsibility for all aspects of the clinical trial, including but not limited to ensuring the signed/approved protocol is followed exactly.

Any deviations from this protocol will be discussed with the Sponsor and appropriately documented. No modifications of the protocol will be permitted without the approval from the Sponsor and the Investigator. Such changes must be documented in writing as soon as possible.

### 7.2 Advertising

If an Investigator chooses to advertise for subjects, whether in professional or consumer publications, radio, television, or any other means, all advertising must be approved by the Sponsor prior to initiation.

### 7.3 Subject Consent

Each subject's parent/legal guardian must sign and date an Informed Consent to allow their child to participate in the clinical trial. Each parent/legal guardian will be given the opportunity to have his/her questions answered to their satisfaction. Without this signed document, a child will be ineligible to participate in this clinical trial.

This consent form will comply with all applicable regulations governing the protection of human subjects. The elements of Informed Consent and the documentation of Informed Consent are specified in ICH GCPs chapter 4. A signed copy of the Informed Consent will be kept by the parent/legal guardian of the child and the Investigator will retain a signed copy

Subjects may withdraw from participation in the clinical trial at any time. Additionally, the Investigator may remove subjects from the clinical trial if it is in the best interest of the subjects. The reason for all Investigator removals from the clinical trial will be documented.

### 7.4 Data Collection

The Principal Investigator is responsible for ensuring that data are collected and reported according to the clinical trial protocol.

#### Data Collection System

A [REDACTED] will be the primary tool used for data collection. [REDACTED]

Additionally, the Electronic Case Report Forms (ECRF) data capture system, a database developed through a validated, Electronic Records/Electronic Signatures (ERES)-compliant

platform (21 CFR Part 11) will be utilized to collect data by the site (e.g., Demographics, Inclusion/Exclusion, Anthropometry, Adverse Events, Medications, General Comments, and Subject Accountability).

All protocol specified data included in the clinical trial database will be collected as e-source.

#### **7.4.1 Source Documents**

Direct data entry will be used via the [REDACTED] and ECRF. The electronic records are considered to be source documents.

There will be periodic monitoring of the site on the critical enrollment days and the study conduct via remote data reviews. Data entered by the parents [REDACTED] [REDACTED] will be monitored periodically to check for compliance via remote monitoring.

### **7.5 Adverse Events or Adverse Device Effects**

An Adverse Event (AE) is defined as any unfavorable and unexpected medical occurrence in a subject. An Adverse Device Effect (ADE) is defined as any AE related to the use of the investigational medical device. This definition includes AEs resulting from insufficient or inadequate instructions for use, any malfunction, use error or intentional misuse of the medical device. Each day (following the initial visit), the parent/legal guardian will be asked if there has been any change in the child's health (illness or injury) since the previous visit or the previous time the questionnaire was filled in. Changes in health will be documented as an AE or ADE as appropriate, regardless of the causality relationship with product use. All AEs and ADEs will be followed to resolution.

#### **7.5.1 Adverse Event and Adverse Device Effect Reporting**

[REDACTED] the parent/legal guardian will be asked twice daily about their child's health and medication intake. Based on the information provided, Sponsor and PI will determine if it is appropriate to record as an Adverse Event or Adverse Device Effect and will contact the parent/legal guardian for more information. Such an occurrence does not necessarily have to have a causal relationship with product use. Due to the nature of this clinical trial, skin irritation in the pant area (diaper rash) will not be documented as an Adverse Event or Adverse Device Effect given it is one of the end points of interest for the clinical trial. However, if a skin reaction occurs in the pant area which causes the parent/legal guardian to seek medical attention, outside the normal follow-up given to the child within the clinical trial, this will be documented and followed in the same manner as other Adverse Events or Adverse Device Effects.

[figure not shown]
The Investigator or designee will review each Adverse Event Report and complete the form based on the following decision charts:

*Chart 1: Categories of ADE and AEs*

Adverse events	Non-device-related	Device- or investigational procedure-related	
Non-serious	Adverse event (AE) a (3.2)	Adverse device effect (ADE) c (3.1)	
Serious	Serious adverse event (SAE) b (3.45)	Serious adverse device effect (SADE) (3.44)	
		Anticipated	Unanticipated
		Anticipated serious adverse device effect (ASADE) c (3.1, Note 1 to entry)	Unanticipated serious adverse device effect (USADE) (3.51)

a Includes all categories.  
b Includes all categories that are serious.  
c Includes all categories that are related to the device or the investigational procedure.

Chart 2: AE categorization flow chart

The Investigator or designee will review each Adverse Event Report and complete the form based on the following definitions:

**Severity:**

- Mild - normal activities unaltered, AE or ADE is annoying, but tolerable
- Moderate - normal activities altered or AE or ADE requires intervention
- Severe - unable to undertake normal activities or is incapacitated

**Investigator's Opinion of Causality:**

- Not Related - there is no medical evidence to suggest that the AE or ADE may be related to product usage
- Doubtful – there is no medical evidence to suggest that the AE or ADE may be related to product usage, or there is another more probable medical explanation

- Possible - there is possible evidence to suggest that the AE or ADE could possibly be related to product usage
- Probable - there is probable evidence to suggest that the AE or ADE is probably related to product usage

**Action Taken by Investigator:**

- None - no change in product usage
- Reduced/Interrupted - product usage reduced or temporarily interrupted
- Discontinued - product usage discontinued.

*Note: Actions taken by parent/guardian may be documented in General Comments.*

The Investigator will decide on a case-by-case basis as to whether any subject should be dropped from the clinical trial. If the Investigator(s) or subject decides to discontinue clinical trial participation, this should be documented and filed with the Sponsor within 72 hours. All adverse events and adverse device effects will be followed until resolution or until the Investigator deems it safe to discharge the subject.

### **7.5.2 Serious or Unexpected Adverse Events or Adverse Device Effects Reporting**

A Serious Adverse Event (SAE) or Serious Adverse Device Effect (SADE) is defined as any unexpected medical occurrence that at any exposure:

1. Results in death
2. Is life-threatening
3. Requires in-patient hospitalization or prolongation of existing hospitalization
4. Results in persistent or significant disability/incapacity
5. Results in a congenital anomaly/birth defect
6. Requires medical or surgical intervention (devices)
7. Is medically significant

All SAEs and SADEs will be recorded on the written and/or electronic SAE or SADE form and tracked in this clinical trial.

The Investigator/Designee must contact the Sponsor within 24 hours to discuss potentially serious or unexpected AEs. During normal business hours: [REDACTED]

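### The AE and SAE/SADE definitions require an event to be unexpected, yet Chart 1 contains an anticipated SADE class

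*Combined protocol and SAP*

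**What the plan says.** Section 7.5 defines an AE as "any unfavorable and unexpected medical occurrence in a subject". It adds that an ADE "is defined as any AE related to the use of the investigational medical device", so an ADE carries every condition that applies to an AE.

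Section 7.5.2 says that an SAE or SADE "is defined as any unexpected medical occurrence that at any exposure" meets one of seven listed criteria. Criterion 6 is "Requires medical or surgical intervention (devices". The same section provides that "All SAEs and SADEs will be recorded on the written and/or electronic SAE or SADE form". It also requires contact with the sponsor within 24 hours about AEs that may be serious or that are unexpected, and its title joins the same two words with *or*.

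Chart 1 in Section 7.5.1 divides serious device-related events into an anticipated class, "Anticipated serious adverse device effect (ASADE", and an unanticipated one. Footnote a says that AE takes in every category. Footnote b, on SAE, reads "Includes all categories that are serious". Footnote c, on ADE and ASADE, reads "Includes all categories that are related to the device or the investigational procedure".

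**The concern.** The definitions make *unexpected* a condition of entry to all four terms: AE, ADE, SAE and SADE. Chart 1 treats expectedness as a later step that sorts events already accepted as SADEs. Read literally, a serious device effect that was foreseen is a SADE on the chart and not a SADE in the text.

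The requirement to use the SAE/SADE form sits in Section 7.5.2 beside the restrictive definition, so the status of such an event on that form is unclear. The sponsor-contact rule is worded in terms of AEs, so it inherits the same restriction from Section 7.5.

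Adverse events are part of the evidence for the primary objective (Section 2). They also feed the safety recommendation in the SAP (Attachment B, General Safety, item 1). With about 32 children under Amendment 1, the classification of even one serious event would be noticed. A written safety definition should not depend on which page the site happens to follow.

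**Working it through.** No arithmetic applies. The documents give no event rate, and Section 4.2 says that the sample size rests on practical limits, so the number of affected events cannot be computed. The check is a comparison of text.

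1. **AE and ADE (Section 7.5).** Every AE is unexpected. Every ADE is an AE. Hence every ADE is unexpected.
2. **SAE and SADE (Section 7.5.2).** Every SAE and every SADE is unexpected.
3. **Chart 1 (Section 7.5.1).** The SADEs consist of an anticipated and an unanticipated class. Through the footnotes, the anticipated class also lies within AE (a), SAE (b) and ADE (c).
4. **Together.** In ordinary usage an anticipated event is not unexpected. Steps 1 and 2 then leave the anticipated class empty, while step 3 requires it as a category.
5. **Could one meaning of the word reconcile everything?**
   - If it means *not foreseen*, the definitions conflict with Chart 1. Every AE is then unexpected, so the 24-hour rule covers every AE and its two conditions separate nothing.
   - If it means *untoward*, the definitions agree with Chart 1. The 24-hour rule again covers every AE, and the word adds almost nothing to *unfavorable* in Section 7.5.
   - The 24-hour rule selects among AEs only if the word has a different sense there from the one in the definitions. No single meaning makes the definitions, the chart and the rule all work.
6. **Where it could arise.** Attachment A foresees redness, blisters or sores in exceptional cases. It describes them as not dangerous and as usually needing no treatment. Suppose that one did need treatment, and assume that treatment counts as intervention under criterion 6. Chart 1 would then place it in the anticipated SADE class, while the Section 7.5.2 definition would not admit it. Section 7.5.1 would still have it documented like other AEs or ADEs if the parent sought medical attention. What remains open is whether it goes on the SAE/SADE form and, less clearly, whether the 24-hour contact applies.

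**The case against.** The strongest reply is that nothing depends on the word in practice.

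- **Collection has no expectedness filter.** Section 3.3.3 asks twice daily about illness, injury and medication. Section 7.5 has changes in health documented as AE or ADE as appropriate, whatever the cause. Section 7.5.1 captures skin reactions that lead to medical attention.
- **Classification follows the charts.** Section 7.5.1 has the form completed from the decision charts, and Chart 1 contains the anticipated class. The same section also refers to definitions that follow, but what follows is severity, causality and action taken, so that line does not make the AE definition govern the form.
- **Seriousness alone triggers contact.** The 24-hour rule is worded as an alternative, so any AE that may be serious is covered.
- **No case is identified.** Attachment A names no foreseen serious reaction. A skin reaction grave enough to be serious is arguably not the one that was foreseen, and would then meet Section 7.5.2 as written.
- **Other sources may settle it.** Chart 2, the text of Amendment 2 and the separate ISO 14971 risk assessment could not be seen. Section 7 commits the trial to ISO 14155, and Chart 1 carries what look like clause numbers.

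Most of this stands, and it limits the consequence. It does not reconcile the texts. No visible section gives *unexpected* the sense of *untoward*, and the 24-hour rule helps only once an event has been accepted as an AE.

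A reader might infer that foreseen serious events would drop out of the trial's safety data, or out of the safety comparison in the SAP. The documents do not support that. The collection rules above would probably record the event, and the SAP lists product-related ADEs and AEs regardless of which serious-event form is used. Nor does the wording explain why ordinary pant-area irritation is not recorded as an AE. Section 7.5.1 handles that separately because irritation is an endpoint.

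**Conclusion.** The inconsistency is real and the concern holds in a limited form. Sections 7.5 and 7.5.2 make unexpectedness a condition of being an AE, ADE, SAE or SADE. Chart 1 puts an anticipated class inside all of them, and Section 7.5.2 itself uses the word as if only some AEs were unexpected.

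The effect is confined to whether a foreseen serious event counts as an SAE or SADE for the dedicated form and for sponsor contact. No lost event is shown, no foreseen serious device reaction is named, and no analysis or sample size changes. The practical effect is probably small, and the point merits consideration as a low-cost correction.

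The conclusion assumes that *unexpected* and *anticipated* carry their ordinary meanings, and that neither Chart 2 nor Amendment 2 already resolves the matter. The Amendment 1 text does not touch these definitions. The example of a treated skin reaction further assumes that treatment counts as intervention; the inconsistency itself does not depend on that.

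**What to change.** Reconcile Sections 7.5 and 7.5.2 with Chart 1:

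- Remove *unexpected* from the AE definition and from the SAE/SADE definition, for example by writing *untoward medical occurrence, whether or not anticipated*.
- Keep expectedness only as the Chart 1 step that separates anticipated from unanticipated SADEs.
- Add one sentence stating that SAE/SADE recording and sponsor contact apply to serious events whether or not they were anticipated.
- If Chart 2 or Amendment 2 already does this, a cross-reference is enough.

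The Section 7.5.1 rule on ordinary pant-area irritation needs no change. The cost is one word in each of two sentences, one added sentence in an amendment and a line in site training. The downside is possibly a few more recorded events.

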**Statement of Compliance for Children's Nocturnal Enuresis Devices**

*It is understood that similarity between intended use and indications for use exists between the Procter & Gamble Children's Nocturnal Enuresis Devices and competitor products. Such devices serve as morphotypes. Procter & Gamble Children's Nocturnal Enuresis Devices when used under the conditions and for the purposes intended, will not compromise the clinical condition or the safety of patients, or the safety and health of users or, where applicable other persons. The benefit of Procter & Gamble Children's Nocturnal Enuresis Devices outweighs the risks associated with the product.*

*Clinical risk identified in risk management has been adequately addressed for use in this clinical trial. This risk associated with the product is very minimal compared to the benefits of the product. Clinical investigation performed on similar Procter & Gamble [REDACTED] pants identified no serious adverse events and no withdrawals due to adverse events. Procter and Gamble [REDACTED] pants were well tolerated by the subjects with no product-related adverse events.*

*Procter & Gamble Children's Nocturnal Enuresis Devices are very simple devices and easy to use. No specific training is required to use this product. There is full consistency between current knowledge/ the state of the art, the available clinical data, the information materials supplied by the manufacturer, and the risk management documentation for Procter & Gamble Adult Children's Nocturnal Enuresis Devices.*

As with any absorbent pant or diaper, it is possible in exceptional cases that these products may cause skin reactions like redness, blisters, or sores. These skin reactions are usually temporary and usually need no medical treatment, nor are they dangerous to the health. The risk of allergies cannot be totally excluded but can be considered very unlikely for these products. For subjects in this clinical trial, we do not expect any further risks apart from potential skin reactions (like redness). In case your child has some skin reactions (redness, swelling or blisters) during this test that concerns you, please contact the clinical trial personnel.

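### Seriousness criterion 6 has no threshold and shares its trigger with Moderate severity, so minor treated events can be classed as SAEs or SADEs

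*Combined protocol and SAP*

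**What the plan says.** Section 7.5.2 says that an SAE or SADE "is defined as any unexpected medical occurrence that at any exposure" meets one of seven listed criteria. Criterion 6 reads "Requires medical or surgical intervention (devices"). The bracketed word is not explained. Events that may be serious or unexpected must be discussed with the sponsor within 24 hours, and SAEs and SADEs go on a dedicated form.

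The severity scale in 7.5.1 has this middle grade: "Moderate - normal activities altered or AE or ADE requires intervention".

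Section 7.5 defines an ordinary AE as "any unfavorable and unexpected medical occurrence in a subject".

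For rash, 7.5.1 sets a default and an exception. By default, "skin irritation in the pant area (diaper rash) will not be documented as an Adverse Event or Adverse Device Effect". The exception is a skin reaction that "causes the parent/legal guardian to seek medical attention, outside the normal follow-up given to the child within the clinical trial"; it is then recorded and followed like any other event.

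Chart 1 in 7.5.1 divides events by seriousness and by relation to the device or procedure, and splits serious device effects into anticipated and unanticipated. Chart 2, a categorization flow chart, appears in the supplied text only as a caption.

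In Attachment A, the Statement of Compliance says that clinical investigation of similar pants "identified no serious adverse events and no withdrawals due to adverse events". The text introducing it says that it will be updated from the outcome of this trial.

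**The concern.** A seriousness rule should separate grave events from ordinary ones. Criterion 6 as written does not, because almost any event that needs a prescription could be said to need medical intervention. The severity scale treats the same need as the mark of a middle grade. An investigator working from the written definitions has no stated point at which a treated event stops being only Moderate and becomes serious as well.

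Two things are at stake. The first is the accuracy of the safety record. The primary objective is in-use tolerability, judged partly on adverse events, and the Statement of Compliance uses the absence of serious events on similar pants as support. A literal reading would overstate serious events in both. The second is consistency. If the site does not apply criterion 6 literally, the classification depends on an unwritten judgement. The investigator or designee completes the event form, and Amendment 1 names only the sponsor's statistician and a substitute clinical scientist as blinded. The person judging can therefore know which product the child was wearing.

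**Working it through.** The plan gives no figure on this point, so the check sets the definitions side by side and runs typical events through them.

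**Is the trigger shared?** Moderate (7.5.1) applies if activities are altered *or* intervention is required. Criterion 6 (7.5.2) applies if medical or surgical intervention is required. Any event that is Moderate because it required medical intervention therefore meets criterion 6 as well. The overlap covers that branch only; an event that is Moderate solely because activities were altered does not meet criterion 6.

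**Does another word in 7.5.2 restore a threshold?**

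- *Unexpected*: the ordinary AE definition in 7.5 uses the same word, so it cannot separate serious from non-serious. Chart 1 also has a class for anticipated serious device effects, so the word is not a firm gate for SADEs.
- *Requires*: the Moderate grade uses the same verb. It excludes treatment that was given but not needed, but draws no line between the two scales.
- *The bracketed word*: if it means that the criterion applies in device studies, it excludes nothing here. If it limits the criterion to device-related events, a treated product-related rash still falls within it. The text does not say which.

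**Five events, classified from the text:**

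1. Ear infection (an acute condition named in INCL02) that required medical treatment: an AE, Moderate through the intervention branch, and criterion 6 is met on a literal reading. Result: SAE.
2. Pant-area rash managed at home or within trial follow-up: not an AE or ADE under 7.5.1. Result: cannot be an SAE or SADE.
3. Pant-area rash taken to outside medical attention, no treatment required: recorded, but criterion 6 is not met.
4. Pant-area rash judged related to the test product, taken to outside medical attention, treatment required: an ADE, and criterion 6 is met. Result: SADE, provided it counts as unexpected. That is open, because Attachment A names redness, blisters and sores in advance.
5. Illness that altered activities but required no medical or surgical intervention: Moderate, criterion 6 not met.

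Events 1 and 4 show the problem. Events 2, 3 and 5 show its limits.

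**Scale.** Amendment 1 plans about 32 children, and section 3.2.2 has 45 days of questionnaires: 32 × 45 = 1,440 child-days, and 1,440 / 365.25 = 3.94 child-years if all complete. The documents give no rate of medically treated illness. Purely as an assumption, 0.5 to 1.5 such illnesses per child-year would give 3.94 × 0.5 = 2.0 to 3.94 × 1.5 = 5.9 events of type 1. This range is illustrative, and the conclusion does not rest on it.

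**The case against.** The strongest reply is that nothing here contradicts anything. Severity and seriousness are different scales, Chart 1 splits by seriousness and relatedness rather than by severity, and an event may properly be both Moderate and serious. This stands. A reader might infer that the two sections cannot both be applied; they can. What remains is that the shared trigger has no qualifier.

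A reader might also infer that any treated rash becomes a SADE. Section 7.5.1 rules that out: rash that is not taken to outside medical attention is not recorded as an AE or ADE at all. Even after such a visit, treatment must have been required, the event must be related, and it must count as unexpected.

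Third, Chart 2 is not shown and could contain the missing threshold. This is a fair limit on what can be claimed. It does not remove the point, because the investigator is also told to complete the form from the written definitions, and these should match the chart.

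Fourth, the effect on the analysis is modest. Under General Safety, the SAP specifies a summary listing of product-related events by treatment period and an expert recommendation, with no SAE count, limit or test. An unrelated ear infection would be outside a product-related listing. The same definition applies in both periods, and the literal error is over-reporting, which is the cautious direction. All this stands, and it rules out calling SAE counts a headline result of the plan. A related, treated rash does enter the listing, however, and the Statement of Compliance speaks of serious events without limiting them to related ones.

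**Conclusion.** The point holds in limited form. In the supplied text, criterion 6 has no threshold and shares its trigger with one branch of Moderate. Applied as written, it can class a medically treated minor illness as an SAE, and a related rash treated after outside medical attention as a SADE. That would overstate serious events in the safety evidence and, for related events, in the SAP listing.

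The number of affected events cannot be derived from the documents. The range of about 2 to 6 shown above depends wholly on an assumed illness rate and on full follow-up, and should not be cited as a finding. In a trial of about 32 children, one reclassified event is enough to change a statement that no serious events occurred.

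The conclusion assumes that Chart 2 carries no qualifier and that the bracketed word does not narrow the criterion. If either does, the written definition still needs to say so. This is more than missing detail, because a stated rule gives the wrong class when followed exactly. It is correctable wording and not a flaw in the design.

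**What to change.** - In 7.5.2, qualify criterion 6 so that the medical or surgical intervention must be needed to prevent an outcome listed in criteria 1 to 5.
- Explain the bracketed word or delete it.
- In 7.5.1, state that severity is graded independently of seriousness, and that needing intervention under Moderate does not by itself make an event serious.
- Confirm that Chart 2 applies the same rule, and align it if it does not.

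The cost is a few sentences, with no added visit, assessment or procedure. The trade-off is that slightly fewer events would be routed to 24-hour reporting. Criterion 7, for medically significant events, stays in place to cover other important cases.
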